15.4. Data Handling and Record Keeping

An electronic case report form (eCRF) is required and must be completed for each included participant.

The investigator or designee may maintain records separate from the case report forms in the forms of clinic charts, medical records, original laboratory, radiology and pathology reports, pharmacy records, etc. The investigator will document in the clinic chart or medical record the date on which the patient signed informed consent prior to the patient's participation in the trial. Source documents must completely reflect the nature and extent of the patient's medical care, and must be available for source document verification against entries in the case report forms when a designee of the Data Safety Monitoring Committee (DSMC) of the Vanderbilt-Ingram Cancer Center (VICC) audits the investigational site. Source documents regarding procedures such as scans and laboratory evaluations performed as part of the standard of care prior to enrollment in the study can be used to fulfill certain screening and baseline assessments. All

information obtained from source documents will be kept in strict confidentiality. Source data sent as supporting documentation to regulatory authorities for serious adverse events will be de-identified to preserve confidentiality.

To enable evaluations and/or audits from Health Authorities and Vanderbilt the investigator agrees to keep records including: The identity of all participants (sufficient information to link records; e.g., hospital records), all original signed informed consent forms, copies of all source documents, and detailed records of drug disposition. To comply with international regulations, the records should be retained by the investigator in compliance with regulations.

During data entry, range and missing data checks will be performed online. The checks to be performed will be documented in the Data Monitoring Plan for the study. A summary report (QC Report) of these checks together with any queries resulting from manual review of the eCRF's will be generated and transmitted to the site and the site monitor. Corrections will be made by the study site personnel. This will be done on an ongoing basis.

16. REGULATORY CONSIDERATIONS

16.1. Pre-Study Documentation

Prior to initiating the trial, the investigator will secure the following documents:

- A signed FDA Form 1572
- A current *curriculum vitae* for the Principal Investigator and each sub-investigator listed on the FDA Form 1572
- A copy of the current medical license for the investigator and each sub-investigator listed on the FDA Form 1572
- A letter from the IRB stipulating approval of the protocol, the informed consent document and any other material provided to potential trial participants with information about the trial (e.g. advertisements)
- A copy of the IRB-approved informed consent document
- The current IRB membership list for the reviewing IRB
- A completed financial disclosure form for the investigator and all sub- investigators
- Current laboratory certification for the reference laboratory and curriculum vitae of the laboratory director
- A list of current laboratory normal values for the reference laboratory.

16.2. Protocol Review and Amendments

Information regarding study conduct and progress will be reported to the Institutional Review Board (IRB) per current institutional standards.

The trial will not be initiated until there is approval by the local IRB of the protocol, informed consent document and any other material used to inform the patient about the nature of the trial. The IRB should be duly constituted according to local regulatory requirements. The investigator will inform the IRB of the progress of the trial at least yearly.

Any changes to the protocol will be made in the form of a written amendment and must be approved by both EMD Serono and the IRB prior to local implementation. All amendments will also be submitted as necessary to the FDA by the Sponsor.

Protocol changes to eliminate an immediate hazard to a trial patient may be implemented by the investigator immediately. The investigator must then immediately inform the local IRB and the FDA.

The Protocol Chair (or designee) is responsible for the coordination and development of all protocol amendments, and will disseminate this information to the institutional participants.

16.3. Informed Consent

The investigator (or his/her designee) will explain to each subject the nature of the study, its purpose, the procedures involved, the expected duration, the potential risks and benefits involved and any discomfort it may entail. Each subject will be informed that participation in the study is voluntary, that s/he may withdraw from the study at any time, and that withdrawal of consent will not affect subsequent medical treatment or relationship with the treating physician(s) or institution. The informed consent will be given by means of a standard written statement, written in non-technical language, which will be IRB approved. The subject should read and consider the statement before signing and dating it, and will be given a copy of the document. No subject will enter the study or have study-specific procedures done before his/her informed consent has been obtained.

In accordance with the Health Information Portability and Accountability Act (HIPAA), the written informed consent document (or a separate document to be given in conjunction with the consent document) will include a subject authorization to release medical information to the study sponsor and supporting agencies and/or allow these bodies, a regulatory authority, or Institutional Review Board access to subjects' medical information that includes all hospital records relevant to the study, including subjects' medical history.

16.4. Ethics and GCP

This study will be carried out in compliance with the protocol and Good Clinical Practice, as described within:

1. ICH Harmonized Tripartite Guidelines for Good Clinical Practice 1996.
2. US 21 Code of Federal Regulations dealing with clinical studies (including parts 50 and 56 concerning informed consent and IRB regulations).
3. Declaration of Helsinki, concerning medical research in humans (Recommendations Guiding Physicians in Biomedical Research Involving Human Subjects, Helsinki 1964, amended Tokyo 1975, Venice 1983, Hong Kong 1989, Somerset West 1996).

The investigator agrees to adhere to the instructions and procedures described within the above and thereby to adhere to the principles of Good Clinical Practice with which the above conform.

16.5. Confidentiality

It is the responsibility of the investigator to insure that the confidentiality of all patients participating in the trial and all of their medical information is maintained. Case report forms (CRFs) and other documents submitted to regulatory authorities must not contain the name of a trial patient. All patients in the trial will be identified by a unique identifier which will be used on all CRFs and any other material submitted to regulatory authorities. All case report forms and any identifying information must be kept in a secure location with access limited to the study staff directly participating in the trial.

16.6. Records Retention

The investigator will retain the records of the clinical trial (including, but not necessarily limited to, CRFs, source documents, informed consent forms, drug accountability records, IRB correspondence, etc) for at least 2 years after all investigations have been discontinued. Study records must be stored in a safe and secure location permitting timely retrieval, if necessary.

Study records that must be retained include case report forms, signed informed consents, correspondence with the IRB, study drug dispensing and inventory records, source documents (clinic charts, medical records, laboratory results, radiographic reports) and screening/enrollment logs.

16.7. Study Termination

The investigator reserves the right to terminate the study at any site and at any time. Reasons for study termination may include, but are not limited to, the following:

- Investigator non-compliance with the protocol, GCP or regulatory requirements
- Insufficient enrollment
- Safety concerns
- Decision by EMD Serono to modify or discontinue the development or manufacture of avelumab
- A request to discontinue the study by the IRB or FDA.

The investigator will promptly notify EMD Serono, the IRB and FDA if the study is terminated for any reason.

17. STATISTICAL CONSIDERATIONS

17.1. Study Design / Endpoints

The primary objective of this clinical trial is to estimate the objective response rate (ORR) from the best response a patient experiences prior to progression (using RECIST v1.1 and irRC). Twenty-five patients will be enrolled on this clinical trial. This regimen will be considered sufficiently active to

warrant further study in more definitive trials if 4 patients experience an objective response among 25 treated.

17.2. Sample Size / Accrual Rate

This investigator-initiated study intends single-site enrollment limited to patients at Vanderbilt University Medical Center.

About 25 patients evaluable for disease response are anticipated to enroll in approximately 24-36 months.

17.3. Statistical Analysis Plan

Demographic, baseline patient characteristics, and study outcomes are intended to be summarized graphically and numerically. Adverse events will be classified by type, incidence, severity and causality according to CTCAE v4.03. All adverse events will be summarized by patient, and all patients who received at least one cycle of the therapy (or discontinued due to treatment-related adverse event) will be included in the safety profile.

Continuous (e.g. age at on-study date) variables will be summarized using the 25th, 50th (median), and 75th percentiles, the range, as well as the mean and standard deviation. Categorical variables, (e.g. adverse events) will be reported as frequencies. 95% confidence intervals will be reported for all outcomes. The distribution of PFS and OS will be estimated using the Kaplan-Meier (product-limit) estimate with standard errors based on Greenwood's formula. No comparative statistical tests are planned for this study.

The Wilson 95% confidence intervals for 0 to 13 objective responses among 25 patients treated are listed in **Table 3**:

Table 3. Ninety-five percent (Wilson) confidence intervals for objective response rate among 25 patients.			
Number of Objective Responses	Objective Response Rate (%)	Lower Limit (%)	Upper Limit (%)
0	0	0	13.3
1	4	0.2	19.5
2	8	2.2	25.0
3	12	4.2	30.0
4	16	6.4	34.6
5	20	8.9	39.1
6	24	11.5	43.4
7	28	14.3	47.6
8	32	17.2	51.6
9	36	20.2	55.5
10	40	23.4	59.3
11	44	26.7	62.9
12	48	30.3	66.5
13	52	33.5	70.0

Considering the published data^{47,48} regarding the responses to standard of care chemotherapy regimens, we propose that observing the same or better clinical outcomes with avelumab monotherapy would warrant further therapeutic study in patients with advanced small intestinal adenocarcinoma.

Twenty-five patients will be enrolled on this clinical trial. We assume a one-sided type I error rate of 5% using a one-sample binomial test and desire 80% power to reject the null hypothesis that this regimen is ineffective if it elicits an objective response rate of 5%. Twenty-five patients provide 80% power to reject the null hypothesis if the true objective response rate (ORR) of this regimen is 21% or greater. This regimen will be considered sufficiently active to warrant further study in more definitive trials if 4 or more patients among 25 treated experience an objective response.

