2.3. Treatment and Dose Rationale

Investigational avelumab will be provided by EMD Serono Research & Development Institute, Inc.

Treatment will consist of cycles lasting 14 days (2 weeks). Each patient will be treated with 10 mg/kg avelumab, administered as 1-hour intravenous (IV) infusion once every two weeks (Q2W).

As additionally addressed below in Section 4.5, based on pharmacokinetic, pharmacodynamic, receptor occupancy, and preliminary clinical safety and efficacy data, biweekly 10 mg/kg is the recommended dose administered to more than 480 patients in the ongoing dose-expansion phase of study EMR 100070-001 (NCT01772004): *A Phase I, Open-label, Multiple-ascending Dose Trial to Investigate the Safety, Tolerability, Pharmacokinetics, Biological and Clinical Activity of Avelumab (MSB0010718C) in Subjects With Metastatic or Locally Advanced Solid Tumors and Expansion to Selected Indications.*

Avelumab will be administered on Day 1 of each cycle after all assessments and procedures have been completed as described in the Schedule of Assessments table (Section 7). In general, it intended that patients will be treated until disease progression or intolerable toxicity.

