3. OBJECTIVES

3.1. Primary Objectives

- To describe any antitumor activity of avelumab monotherapy, as measured by the response rate in patients with advanced or metastatic small intestinal adenocarcinoma.
- To describe the safety profile of avelumab monotherapy in patients with advanced or metastatic small intestinal adenocarcinoma.

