13.1. Definitions

For purposes of this study, patients should be re-evaluated for response every 8 weeks. Response and progression will be evaluated using the international criteria proposed by the revised Response Evaluation Criteria in Solid Tumors (RECIST) Committee (version 1.1) and immune-related response criteria (irRC). Any evaluable or measurable disease must be documented at screening and reassessed at each subsequent tumor evaluation. If a patient is found to have disease progression by RECIST, at the discretion of the treating physician, the patient may remain on study. Baseline evaluation of disease status by CT or MRI required within 28 days prior to first dose of avelumab. The first scheduled re-scan should be performed and evaluated 7 to 8 weeks after Cycle 1, Day 1 treatment, with subsequent scheduled scans intended every 8 to 9 weeks thereafter. If progression is confirmed by irRC, the patient should typically be removed from study (i.e. in the absence of therapeutic benefit and an alternative agreement and arrangement specified by protocol). If irRC show the patient to not have disease progression, the patient may remain on study.

Evaluable for toxicity: All patients will be evaluable for toxicity from time of their first treatment with avelumab.

Evaluable for objective response: Only those patients who have measurable disease present at baseline, have received at least one cycle of therapy, and have had their disease re-evaluated will be considered evaluable for response. These patients will have their response classified according to the definitions stated below. (Note: Patients who exhibit objective disease progression prior to the end of cycle 1 will also be considered evaluable.)

If a patient discontinues study treatment for reasons clearly not related to study treatment, after completing fewer than one planned infusion of avelumab, and/or receiving <75% of the total intended dose of avelumab over the first cycle of treatment + an additional 14 days (i.e. first 28 days after initiating patient's first dose of avelumab), then that patient will be considered not evaluable for response to study treatment and may be replaced with a new patient.

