17.4. Reporting and Exclusions

All patients included in the study must be assessed for safety, tolerability, and response to treatment, even if there are major protocol treatment deviations or if they are ineligible. Each patient will be assigned one of the following response categories: 1) complete response, 2) partial response, 3) stable disease, 4) progressive disease, 5) early death from malignant disease, 6) early death from toxicity, 7) early death because of other cause, or 9) unknown (not assessable, insufficient data).

All patients meeting the eligibility criteria and received study drug for 2 weeks should be included in the main analysis of the clinical benefit rate. Patients in above response categories 4-9 should be considered to have a treatment failure (disease progression). Thus, an incorrect treatment schedule or drug administration should not result in exclusion from the analysis of the response and clinical benefit rate.

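### The safety set in Section 17.3 is narrower than the one in Section 13.1: below one cycle, a dosed patient enters only if the reason for stopping is judged treatment-related

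*Combined protocol and SAP*

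**What the plan says.** Safety is one of the two primary objectives in Section 3.1: "To describe the safety profile of avelumab monotherapy in patients with advanced or metastatic small intestinal adenocarcinoma". Section 17.3 reports adverse events (AEs) as frequencies and adds that "95% confidence intervals will be reported for all outcomes". The only sentence in 17.3 that says who enters the safety summary is this one: "all patients who received at least one cycle of the therapy (or discontinued due to treatment-related adverse event) will be included in the safety profile".

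Two other sections describe the same population differently. Section 13.1: "All patients will be evaluable for toxicity from time of their first treatment with avelumab". Section 17.4: "All patients included in the study must be assessed for safety, tolerability, and response to treatment", and it adds that neither ineligibility nor a major treatment deviation is a reason to be left out.

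Section 17.3 does not define one cycle. Section 2.3 sets the cycle length at 14 days, with one infusion on Day 1. Attribution is the investigator's judgement on a five-point scale (Section 14.4.2). For binary regulatory reporting, the category Unlikely is grouped with Unrelated.

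On the collection window, Section 14.1 collects AEs through the study and within 30 days of the last dose, and extends contact for ongoing related events. Section 7.1 note 17 and Section 7.6 require safety follow-up to 90 (+3) days after the last dose because of delayed immune-related toxicity.

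**The concern.** A dosed patient who falls short of one cycle is in the 13.1 set whatever the reason for stopping. Under 17.3 the same patient is named only if the stop was due to a treatment-related AE. Two analysts could each follow the plan and report different denominators.

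The trial has one arm, so there is no control group against which to judge causality. A safety denominator that turns on attribution, even for a few patients, uses the least certain judgement in the dataset to decide whose events are counted. The safety description is a primary objective and is reported with confidence intervals, so the denominator should be fixed before the data are seen.

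**Working it through.** **The plan's own figure.** The only power statement is 80% at a true response rate of 21%, for the rule of 4 or more responses in 25 against a null of 5% (Section 17.3). Exact binomial: P(X ≥ 4 | n = 25, p = 0.05) = 0.0341 and P(X ≥ 4 | n = 25, p = 0.21) = 0.8013. The stated power reproduces. It concerns response only, so the safety set does not affect it.

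**The rules side by side, for dosed patients.**

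| Patient | 13.1 | 17.3, cycle = 14 days completed | 17.3, cycle = one infusion |
|---|---|---|---|
| Full first infusion, stops by day 14, AE judged related | in | in | in |
| Full first infusion, stops or dies by day 14, cause judged unrelated | in | not named | in |
| Incomplete first infusion, stopped for AE judged related | in | in | in |
| Incomplete first infusion, stopped for unrelated cause | in | not named | not named |

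The parenthesis in 17.3 has a purpose only if some dosed patients fall short of one cycle. For those patients, entry depends on attribution under either reading.

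**Which reading of one cycle?** Section 13.1 separates first treatment (toxicity) from at least one cycle (response) and adds that "Patients who exhibit objective disease progression prior to the end of cycle 1 will also be considered evaluable". That wording treats a cycle as a period with an end and favours 14 days. In the other direction, each cycle contains a single Day 1 infusion, and where 17.4 means elapsed time it says 2 weeks. The documents do not settle it.

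**Does the plan foresee such patients?** Sections 5.5 and 13.1 allow replacement of patients who stop for clearly unrelated reasons after less than one planned infusion, and/or with under 75% of the intended dose in the first 28 days. Two infusions are intended in that time (days 1 and 15), so one infusion alone is 1/2 = 50%. Replacement concerns response evaluability and does not remove anyone from toxicity evaluation under 13.1.

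**Size.** The documents give no count of early leavers, so the counts here are assumptions: 25 dosed, k patients left out, each with the event, and no other patient with it. The intervals are plain Wilson 95% intervals, with centre (p + z²/2n)/(1 + z²/n), half-width z·√(p(1−p)/n + z²/4n²)/(1 + z²/n) and z = 1.96.

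| k | All dosed | 17.3 set |
|---|---|---|
| 1 | 1/25 = 4.0% (0.7 to 19.5) | 0/24 = 0% (0 to 13.8) |
| 2 | 2/25 = 8.0% (2.2 to 25.0) | 0/23 = 0% (0 to 14.3) |
| 3 | 3/25 = 12.0% (4.2 to 30.0) | 0/22 = 0% (0 to 14.9) |

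For k = 1 the shift is 4.0 points against an interval width of 19.5 − 0.7 = 18.8 points. (Table 3 prints 0.2 as the lower limit for 1 of 25. Nothing here depends on that difference.) If the omitted patient had no event and one other patient did, the rate moves up, from 1/25 = 4.0% to 1/24 = 4.2% (0.7 to 20.2). If the omitted patient is replaced, the first comparison becomes 1/26 = 3.8% against 0/25 = 0%.

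**Collection window.** Section 14.3.1 ties newly emerging AEs to the reporting period that 14.1 sets. Related serious AEs (SAEs) after that period are covered: 14.5.10 requires reporting with no end date, and 14.1 asks for serious post-study events that might reasonably be related. Ongoing related AEs are followed under 14.1. Section 14.5.13 asks for all SAEs regardless of causality but states no window, and 14.5.12 gives AEs of special interest (AESIs) no window of their own. That leaves new non-serious AEs and AESIs, and SAEs judged unrelated, with onset on days 31-90.

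**The case against.** The strongest reply is that 17.3 excludes nobody in terms. It says who will be included and does not say only. The same sentence begins by promising that all AEs are summarised by patient, and 13.1 and 17.4 cover everyone else. The parenthesis adds patients, namely those stopped by toxicity, whose loss would matter most. A patient who leaves for progression or withdrawal fails the cycle test, not a causality test.

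Much of this stands. It shrinks the affected group, and on the one-infusion reading the group is nearly empty. Section 17.4 says assessed rather than included in the safety profile, so 13.1 is the sharper conflict. But an analyst building the tables from 17.3 would still use a different rule from 13.1, and below one cycle that rule rests on attribution.

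Three stronger readings are tempting and are not supported:

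- A reader might infer that treatment-related toxicity would be materially understated. A patient stopped by a related event is kept by the parenthesis. A related event is lost only if the patient had one during the first cycle and then left for a different, unrelated cause.
- A reader might take the 17.4 response category "7) early death because of other cause" as showing that deaths within 14 days are expected. The plan does not define early, and the first re-scan is at 7 to 8 weeks.
- A reader might infer that delayed immune-related events after day 30 are not captured at all. Related late SAEs and ongoing related AEs are captured, and the reference in 14.1 to collection throughout the study is not a clean cut-off.

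**Conclusion.** The conflict between 17.3 and 13.1 is real and should be corrected, but its consequence is modest. The size of the affected group depends on what one cycle means: possibly a few patients if it is 14 completed days, almost none if it is one infusion. The documents give no rate of early departure, so the effect cannot be estimated. The 4.0% against 0% comparison is an illustration on assumed counts. The three-patient row is an extreme case, because every omitted patient has the event and no one else does. The bias can go either way, the safety summaries are descriptive, no comparative test rests on them, and the response-rate power stays at 80%.

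The 30-day against 90-day point is secondary. It is a gap in wording about new non-serious AEs and AESIs, and SAEs judged unrelated, on days 31-90. It does not show that late toxicity goes unmonitored.

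**What to change.** In Section 17.3, define the safety set as all patients who received any amount of avelumab, regardless of treatment duration, reason for stopping or attribution, in line with Section 13.1. Use that set as the denominator for every AE frequency and interval. This costs one sentence and needs no extra patients or visits.

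In Section 14.1, add one sentence or cross-reference reconciling the 30-day window with Section 7.1 note 17, Section 7.6 and Section 14.5. It should say whether new non-serious AEs and AESIs, and SAEs judged unrelated, found on days 31-90 are recorded and tabulated. If they are, the cost is a little more data entry at a contact the plan already requires. Those events are also harder to interpret once another therapy has started, so showing them separately would be sensible but is optional.
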